9.4.2 METHOD OF ASSIGNING PATIENTS TO TREATMENT GROUPS

The Research Coordinator will determine the scheduling:

If you participate, your time commitment will include six one hour appointments with your study staff. These appointments will be on a weekday day, at 11:00am, 12:00 noon or 2:00pm. As a participant, you will be assigned to on weekday for a one hour appointment for six consecutive weeks. Please put an X beside each time that works for you on each day.

Monday@		11:00am;		12:00 noon;		2:00pm
Tuesday@		11:00am;		12:00 noon;		2:00pm
Wednesday@		11:00am;		12:00 noon;		2:00pm
Thursday@		11:00am;		12:00 noon;		2:00pm

Treatment providers will be required to declare at least one and preferably two of these times (11am, noon and/or 2pm) as times they will be available to delivery treatment, given two week notice of a participant being assigned. The Research Coordinator will make effort to inform each provider when it is likely they will be assigned a new participant.

The Research Coordinator will inform the treatment provider one week in advance of a probably participant being assigned, also informing the treatment provider of the treatment to be utilized (FOA, CBT-I, Combined and Sleep Hygiene).

The Research Coordinator will keep an Excel spread sheet in order to systematically assign subjects (participants) to treatment. Participants will be randomly assigned to treatment and then assigned to the next treatment provider in a systematic, non-biased manner. The first four treatment providers will be randomly designated by the Research Coordinator as the first, second, third or fourth treatment provider to be assigned the participant. The first participant in the clinical trial will go to the provider declared first to be assigned. The second participant in the clinical trial will go to the provider declared second to be assigned. Similarly for assignment of a participant to the third and fourth provider, the fifth participant will be assigned to the provider who had been randomly designated as the first to be assigned a participant. The assignment will proceed, sixth participant to the provider who had been assigned the second participant in the study, etc. The Research Coordinator will use Excel spread sheet in order to determine which treatment provider is next to be assigned a participant.

At the end of the In Person Screening and Data Gathering, the Research Coordinator will inform the participant of the time and date of their first treatment session and the name of the treatment provider.

The Research Coordinator will direct the participant to arrive a few minutes early and to check in at the front desk in the first floor reception area. The participant will be told to tell the receptionist their name, the name of their treatment provider, and that they are receiving treatment for insomnia in the Insomnia Clinical Research Trial.

The Research Coordinator will schedule the participant with one of the treatment providers. The treatment will be at either 11:00am, 12 noon or 2:00pm depending on which one hour block of time that treatment provider has reserved for treatment delivery. The Research Coordinator will schedule the initial session in Practice Fusion with 5 weekly repeats. The Research Coordinator will then send an email to the treatment

provider indicating the name of the client, the time and date on which the first session is scheduled, and the treatment the provider is to deliver (FOA, CBT-I, Combined and Sleep Hygiene).

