Puget Sound Psychiatry Center
[name]
[name]

**“A Randomized, Open Label, Sleep Hygiene Controlled 6-Week
Study to Compare the Efficacy of four (CBT-I, FOA, Combined
CBT-I and FOA and Sleep Hygiene) Different Behavioral
Approaches for the Treatment of Adult Subjects with
Insomnia”**

PSPC-17-01
NCT- 03461666

Protocol Date: 02-12-2018
Version 1.2

Confidentiality Statement:

This document is the property of Puget Sound Psychiatry Center (PSPC), Bothell WA and may not—in full or part—be passed on, reproduced, published, distributed, or submitted to any regulatory authority without the express written permission of PSPC.

2.0**SYNOPSIS AND SCHEDULE OF EVALUATIONS**

CLINICAL STUDY SYNOPSIS: Study PSPC-17-01	
Study Number	PSPC-17-01
Title of Study	A Randomized Open Label, Sleep Hygiene Controlled 6-Week Study to Compare the Efficacy of four (CBT-I, FOA, Combined CBT-I and FOA and Sleep Hygiene) different Behavioral Approaches for the Treatment of Adult Subjects with Insomnia.
Study Center (Country)	Puget Sound Psychiatric Center, [name](United States)
Development Phase	Prospective Study
Objective	The current study seeks to evaluate and compare the effectiveness of (1) cognitive behavior therapy for insomnia [CBT-I], (2) focus of attention [FOA], (3) a combination of cognitive behavior therapy for insomnia and focus of attention, and (4) a sleep hygiene control intervention.
Methodology	Allocation: Randomized (1; 1; 1; 1) Intervention Model: Parallel Assignment Primary Purpose: Treatment
Number of Patients	40/group or 160 totals. It is estimated that 320 prospects will need to be screened in order to have 40 per group for a total of 160 participants.

Diagnosis and Main Criteria for Inclusion.	Male and female outpatients who are 18 or older to 72 years. Insomnia Severity Index > or = 10 Meet diagnostic criteria for Insomnia Disorder per DSM-5 Willing and able to sign Informed consent form Not planning on moving away from the area for the subsequent 12 weeks.

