Once the Informed Consent form has been completed, the next step involves a diagnostic interview to assess for Insomnia Disorder. The Research Coordinator reads the bold print script to the prospective participant. See DSM-5 Diagnostic Assessment Interview.

QUESTIONNAIRE AND INVENTORIES

Since this is a clinical research trial, we have a questionnaire and some inventories for you to complete as part of the initial data gathering.

Here is the first one. Give the person the Sleep Measures (SM) questionnaire.

I recommend you use a pencil so you can erase if you make an error. Do you need a pencil?
Be sure the person has a comfortable place to write (a table top, for example).

This is the first one. Go ahead. Take a few minutes to complete it. I'm here if you have any questions.

When the participant has completed the Sleep Measures (SM) questionnaire, check to ensure that all questions have been answered. Be sure questions with numerous options (a-f; -3 to +3; etc.) are clearly answered.

Ask the person to complete the **Insomnia Severity Index (ISI)**.

This will give us important information about your insomnia.

When the participant has completed the inventory, check to ensure that all questions have been answered clearly. Check for ISI > or = 10. If not, the person is not eligible. If still eligible, record their score.

Ask the person to complete the **Beck Depression Inventory (BDI)**.

Depression may or may not be a factor for you. However, this is a research study, and the researchers want to be able to assess whether the treatment effect differs by level of depression.

When the participant has completed the BDI, check to ensure that all questions have been answered clearly. Check for BDI > or = 29. If so, the person is not eligible. If still eligible, record their score.

Similarly explain and ask the person to complete the **Beck Anxiety Inventory (BAI)**. When the participant has completed the BAI, check to ensure that all questions have been answered clearly. Check for BAI > or = 36. If so, the person is not eligible. If still eligible, record their score.

1. **Goal Motivation Scale (GMS)**
2. **Goal Motivation Scale-Insomnia (GMS-I)**
3. **Self-Report Sleep Measures (SRSM)**
4. **Clinical Global Impression (CGI)**
5. **Clinical Global Impression – Severity scale (CGI-S)**
6. **Quality of Life Enjoyment and Satisfaction (Q-LES)**
7. **Columbia Suicide Severity Rating Scale (C-SSRS)**

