9.4.3 CLINICAL PROCEDURES

The study staff will follow the six session protocol for treatment delivery. Each of the six sessions is scripted so as to provide standardization, and the study staff will generally be reading the script. The first session is identical across all four treatments. For specifics, see file folders entitled CBT-I, FOA, Combo and Sleep Hygiene.

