9.4.6.2 RANDAMIZATION OPEN LABEL SLEEP HYGIENE CONTROLLED SIX WEEK STUDY TREATMENT PERIOD

Patients who meet all eligibility criteria at Screening (Visit 1) and who continue to meet all the eligibility criteria for participation in the study at the Baseline Visit (Visit 2) will be assigned a “Participant Number” (PN). The first seven digits will identify the participant with date of birth followed by the first letter in their first name (given at birth). Digits the first three digits will identify the participant. The first participant assigned a PN will be 001. The second participant assigned a PN will be 002, etc. The 4th digit will identify the participant’s gender (M/F). The 5th digit will identify the participant’s treatment type [1 = Focus of Attention (FOA); 2 = Cognitive Behavior Therapy for Insomnia (CBT-I); 3 = Combination of FOA and CBT-I (Combined); and 4 = Placebo (Sleep Hygiene only). Digits 5-6 will identify the primary study staff delivering the treatment. An example might be 01 = [name].

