9.5.3.1 Visit 1 (Screening)

At Screening (Visit 1), study procedures will be reviewed with the patient, and documentation of informed consent will be obtained ([Section 5.3](#)). After informed consent is obtained, patients will be assigned a unique "Participant Number" (PN) ([Section 5.0](#)). A review of inclusion/exclusion criteria and other screening assessments will be conducted to determine the patient's eligibility for enrollment ([Sections 9.3.1](#) and [9.3.2](#)).

At Screening (Visit 1), the following procedures will also be performed:

1. Obtain and record medical (surgical, neurological), psychiatric history
2. Obtain and record prior medication history, nondrug psychiatric treatment history, and current medication status
3. Review of all inclusion/exclusion criteria
4. Administer ISI (Insomnia Severity Index)
5. Administer BAI (Beck Anxiety Inventory)
6. Administer BDI (Beck Depression Inventory)
7. Administer SRSM (Self Report Sleep Measures)
8. Administer WSL (Weekly Sleep Log)

9. Administer CGI-S (Clinical Global Impression –Severity Scale)
10. Administer CGI (Clinical Global Impression)
11. Administer Q-LES (Quality of Life Enjoyment and Satisfaction)
12. Administer C-SSRS (Columbia-*Suicide* Severity Rating Scale)
13. Review concomitant medications

Schedule Visit 2 up to 14 days after Visit 1

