9.5.3.2 Visit 2 (or Baseline Visit)

The Baseline Visit 2 will be conducted up to 14 days after Screening (Visit 1) to determine whether the patient is eligible to continue into the randomization, open label, sleep hygiene controlled 6 week study treatment period.

At the visit 2, the following procedures will be performed:

1. Review of all inclusion/exclusion criteria
2. Administer SRSM (Self Report Sleep Measures)
3. Administer CGI-S (Clinical Global Impression –Severity Scale)
4. Administer CGI (Clinical Global Impression)
5. Administer C-SSRS (Columbia-*Suicide* Severity Rating Scale)
6. Review and record AEs
7. Eligible patients will be assigned an “Participant Number” (PN).

Administer Randomization (must occur after all efficacy and safety assessments)

Schedule Visit 3

9.5.3.3 Visit 3

At Visit 3, the following procedures will be performed:

1. Review of all inclusion/exclusion criteria
2. Administer SRSM (Self Report Sleep Measures)
3. Administer CGI-S (Clinical Global Impression –Severity Scale)
4. Administer CGI (Clinical Global Impression)
5. Administer C-SSRS (Columbia-*Suicide* Severity Rating Scale)
6. Review concomitant medications

Schedule Visit 4

9.5.3.4 Visit 4

At Visit 4, the following procedures will be performed:

1. Review of all inclusion/exclusion criteria
2. Administer SRSM (Self Report Sleep Measures)
3. Administer CGI-S (Clinical Global Impression –Severity Scale)
4. Administer CGI (Clinical Global Impression)
5. Administer C-SSRS (Columbia-*Suicide* Severity Rating Scale)
6. Review concomitant medications

Schedule Visit 5

9.5.3.5

Visit 5

At Visit 5, the following procedures will be performed:

1. Review of all inclusion/exclusion criteria
2. Administer SRSM (Self Report Sleep Measures)
3. Administer CGI-S (Clinical Global Impression –Severity Scale)
4. Administer CGI (Clinical Global Impression)
5. Administer C-SSRS (Columbia-Suicide Severity Rating Scale)
6. Review concomitant medications

Schedule Visit 6

9.5.3.6

Visit 6

At Visit 6, the following procedures will be performed:

1. Review of all inclusion/exclusion criteria
2. Administer SRSM (Self Report Sleep Measures)
3. Administer CGI-S (Clinical Global Impression –Severity Scale)
4. Administer CGI (Clinical Global Impression)
5. Administer C-SSRS (Columbia-Suicide Severity Rating Scale)
6. Review concomitant medications

Schedule Visit 7

9.5.3.7

Visit 7

At Visit 7, the following procedures will be performed:

1. Review of all inclusion/exclusion criteria

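### The treatment provider is told the arm before the stated time of randomization, and then decides final eligibility and Intent-to-Treat membership

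*Protocol*

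**What the plan says.** The synopsis gives the allocation as "Allocation: Randomized (1; 1; 1; 1". On how this is carried out, the protocol says the following.

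- **Who screens.** Section 9.1.2: "The Research Coordinator reads the bold print script to the prospective participant". The coordinator also administers the questionnaires and checks the ISI, BDI and BAI cut-offs.
- **Who allocates.** Section 9.4.2, repeated in section 9.1.2: "The Research Coordinator will keep an Excel spread sheet in order to systematically assign subjects (participants) to treatment".
- **When randomization happens.** Section 9.4 randomizes patients found eligible at the end of Visit 2. The Visit 2 list in section 9.5.3.2 reads "Administer Randomization (must occur after all efficacy and safety assessments".
- **When the provider learns the arm.** Section 9.4.2 has the coordinator notify the provider of a likely participant one week ahead, "also informing the treatment provider of the treatment to be utilized". When session 1 is booked, the coordinator also emails the provider the client's name and the treatment to be delivered.
- **When eligibility is settled.** The script in section 9.1.2 tells the participant that the final decision follows the first meeting with the provider, and depends on the ActiWatch data and the provider's view of the diagnosis.
- **Who enters the Intent-to-Treat Population.** Section 9.7.2 (also the synopsis and section 8) admits those who attend session 1 and whom the provider judges to have Insomnia Disorder.
- **What the Participant Number shows.** Its 5th digit is the "treatment type [1 = Focus of Attention (FOA); 2 = Cognitive Behavior Therapy for Insomnia (CBT-I" and so on through the four arms (sections 9.4.1 and 9.4.6.2). Section 9.5.3.1 issues it at screening: "After informed consent is obtained, patients will be assigned a unique" Participant Number. Sections 9.4.6.2 and 9.5.3.2 issue it at Visit 2, to eligible patients.

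**The concern.** Randomization makes the arms comparable only if nobody who can influence entry knows the arm while entry is still open. Here the provider, whose judgement closes the eligibility question, has the treatment in writing beforehand. A provider who finds a borderline case unsuited to the assigned treatment could, without any ill intent, be quicker to conclude that the diagnosis is not met.

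Because the same judgement defines the Intent-to-Treat Population, such a participant would leave the main analysis set as well as the study. The set would then be selected after allocation by someone aware of the arm. No later adjustment reliably repairs that.

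**Working it through.** No arithmetic applies: the protocol states no figure on this point, and none is needed. The check is to put the steps in order and see what is known at each.

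**Step 1: locate session 1.** Section 9.4.6 places the six sessions at Visits 2 to 7, so session 1 is at Visit 2. That sentence names only sleep hygiene, but the paragraph goes on to cover all four treatments, and I read it as applying to every arm.

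**Step 2: compare the stated time of randomization with the stated time of disclosure.**

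| Event | Where stated | Timing |
|---|---|---|
| Randomization | 9.4, 9.5.3.2 | End of Visit 2, after that visit's assessments |
| Provider notified of the treatment | 9.1.2, 9.4.2 | One week before a likely participant is assigned |
| Provider emailed name and treatment | 9.1.2, 9.4.2 | At booking of session 1, so before Visit 2 |
| Final eligibility decision | 9.1.2 | After session 1 |
| Judgement that decides Intent-to-Treat entry | 9.7.2 | By the provider who holds session 1 |

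An arm assigned at the end of Visit 2 cannot be announced before Visit 2. Either randomization in fact happens earlier than sections 9.4 and 9.5.3.2 say, or the advance notice cannot be given. The document requires both.

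**Step 3: follow the notification text as written.** The order is: screening by the coordinator, treatment sent to the provider, session 1, diagnostic opinion from that provider, final eligibility. The arm is known at the two last steps, where a judgement is made. This result does not depend on when the Participant Number is issued.

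**Step 4: look at the Participant Number separately.** Under section 9.5.3.1 it follows consent and comes before the eligibility review described there. Under sections 9.4.6.2 and 9.5.3.2 it is given at Visit 2 to those still eligible. Even within section 9.5.3.2 it is listed ahead of the randomization line, although a number containing the arm cannot be completed until the arm exists. The format also conflicts with itself: the 5th digit is the treatment, while digits 5-6 are the treating staff.

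**Step 5: look for concealment.** No section says who generates the random sequence, who may see it, or how it is kept from the coordinator or the provider. Section 9.4.2 says assignment to treatment is random, but its detailed procedure concerns the rotation of providers. That rotation does not by itself reveal the arm.

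**The case against.** Several points can fairly be made for the plan.

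- **The protocol already states nearly the right timing.** Randomization at the end of Visit 2, after all assessments, is close to the end of session 1. This stands, and it makes the correction easier. It does not remove the notification text that contradicts it.
- **The Visit 1 issue of the number may be a slip.** A reader might infer that the arm is fixed and visible at Visit 1. The documents do not support that as the rule: only section 9.5.3.1 places the number there, its cross-reference leads to the ethics section, and two other sections say Visit 2. What stands is a conflict to reconcile.
- **The coordinator has little discretion.** The screening cut-offs are numeric, and the script has the coordinator say that they are not a clinician. A reader might also infer that the coordinator can see a pre-generated list of upcoming arms; the text does not say so. Both points stand, which is why the finding rests mainly on the provider. The coordinator matters as the person who screens, keeps the sheet and passes on the arm.
- **The trial is open label.** That excuses knowledge of the arm after allocation, including an identifier that shows it to those handling outcome data. It does not excuse disclosure before entry is settled: concealment until enrolment is separate from blinding afterwards and is possible in an open-label trial.

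**Conclusion.** The allocation procedure contradicts itself on when the arm exists, and it does not keep the arm concealed until eligibility is final. The main weakness is that a provider who already knows the arm gives the diagnostic opinion on which both final eligibility and Intent-to-Treat membership depend. The arm-bearing Participant Number, with two stated times of issue, is a second, lesser weakness.

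The conclusion assumes that the notification steps are carried out as written and that session 1 is at Visit 2 in every arm. It shows that arm-dependent exclusion is possible. A reader might infer that it has occurred, or that an arm mean is shifted by a given amount. The documents support neither: they give no number of participants turned away at session 1 and no measure of how their prognosis would differ. The correction should be made, because the fault lies in the stated procedure and is cheap to remove.

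**What to change.** 1. Have the random sequence generated in advance and held by an existing person who neither screens nor treats. The only statistician the protocol names is the independent one serving the DSMB (section 9.8), so the holder should be identified by role. If blocks are used, their sizes should vary and be undisclosed, because the coordinator will know all past assignments.
2. Release the arm to the coordinator and provider only after final eligibility is recorded at the end of session 1. The design allows this: "The first session is identical across all four treatments" (section 9.4.3). Because the ActiWatch is returned on the day of session 1, its data must be read before eligibility is recorded. If that cannot be done the same day, the arm can be released before session 2, a week later.
3. Delete the treatment from both the one-week notice and the booking email, in sections 9.1.2 and 9.4.2. Notice that a participant is coming can stay.
4. With the diagnosis recorded before the arm is released, define the Intent-to-Treat Population as all randomized participants.
5. Use a sequential Participant Number with no arm digit, and reconcile section 9.5.3.1 with sections 9.4.6.2 and 9.5.3.2 on when it is issued. Dropping the arm digit also ends the digit overlap.

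The cost is a one-time list, a changed identifier format and edits to repeated text. The practical downside is that providers learn the treatment after session 1 instead of a week before it. As sessions are scripted and weekly, they still have time to prepare for session 2 when the arm is released at the end of session 1.

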9.4.3 CLINICAL PROCEDURES

The study staff will follow the six session protocol for treatment delivery. Each of the six sessions is scripted so as to provide standardization, and the study staff will generally be reading the script. The first session is identical across all four treatments. For specifics, see file folders entitled CBT-I, FOA, Combo and Sleep Hygiene.

9.4.4 DATA GATHERING DURING TREATMENT

Ongoing self-report data pertaining to the participant's sleep using a Weekly Sleep Log. Weekly Sleep Logs will be completed by the participant and brought to each treatment session. At the beginning of each session, the study staff will review the Weekly Sleep Log for completion. After the treatment session has ended and during the same day, the study staff will forward the Weekly Sleep Log to the Research Coordinator.

The Research Coordinator will enter the following information onto the DATA SHEET:

1. SL; Sleep Latency (time to fall asleep in minutes)
2. NOA: Number of Awakenings
3. WASO: Wake After Sleep Onset (in minutes)
4. SL + WASO (in minutes)
5. TOB: Total Time Out of Bed in minutes
6. TST: Total Sleep Time (in minutes)
7. TIB: Time In Bed (total, in minutes)
8. SE: Sleep Efficiency = TST/TIB (as a decimal)

9.4.5 END OF TREATMENT

SAFETY FOLLOW UP PERIOD

Coordinated and administered by Research Coordinator. Completed after last treatment session; can be on that day but not before the treatment session; must be no later than one week after that date.

FEEDBACK QUESTIONNAIRE:

1. Beck Depression Inventory (BDI)
2. Beck Anxiety Inventory (BAI)
3. Insomnia Severity Index (ISI)
4. Self Report Sleep Measures (SRSM)
5. Clinical Global Impression (CGI)
6. Clinical Global Impression – Severity scale (CGI-S)
7. Quality of Life Enjoyment and Satisfaction (Q-LES)
8. Columbia Suicide Severity Rating Scale (C-SSRS)

THREE MONTH FOLLOW UP:

WEEKLY SLEEP LOG (WSL)

Data entry completed for one week at each administration [At in person intake, each week during treatment and at 3, 6 and 12 months]

[Each of the following is needed for data entry as an average for the last 7 nights]

1. SL; Sleep Latency (time to fall asleep in minutes)
2. NOA: Number of Awakenings
3. WASO: Wake After Sleep Onset (in minutes)
4. SL + WASO (in minutes)

5. **TOB: Total Time Out of Bed in minutes**
6. **WASO: Waking Time After Sleep Onset in minutes**
7. **TST: Total Sleep Time (in minutes)**
8. **TIB: Time In Bed (total, in minutes)**
9. **SE: Sleep Efficiency = TST/TIB (as a percentage)**
10. **Beck Depression Inventory (BDI)**
11. **Beck Anxiety Inventory (BAI)**
12. **Insomnia Severity Index (ISI)**
13. **Self Report Sleep Measures (SRSM)**
14. **Clinical Global Impression (CGI)**
15. **Clinical Global Impression – Severity scale (CGI-S)**
16. **Columbia Suicide Severity Rating Scale (C-SSRS)**

SIX MONTH FOLLOW UP:

This is the same as the THREE MONTH FOLLOW UP except that the following three are added.

1. **Beck Depression Inventory (BDI)**
2. **Beck Anxiety Inventory (BAI)**
3. **Insomnia Severity Index (ISI)**
4. **Self Report Sleep Measures (SRSM)**
5. **Clinical Global Impression (CGI)**
6. **Clinical Global Impression – Severity scale (CGI-S)**
7. **Columbia Suicide Severity Rating Scale (C-SSRS)**

TWELVE MONTH FOLLOW UP:

This is the same as the SIX MONTH FOLLOW UP adding the Feedback Questionnaire.

1. **Beck Depression Inventory (BDI)**
2. **Beck Anxiety Inventory (BAI)**
3. **Insomnia Severity Index (ISI)**
4. **Self Report Sleep Measures (SRSM)**
5. **Clinical Global Impression (CGI)**
6. **Clinical Global Impression – Severity scale (CGI-S)**
7. **Columbia Suicide Severity Rating Scale (C-SSRS)**

A schematic of the study design is presented in [Figure 9.1-1](#). The Schedule of Evaluations is presented in Section [2.0](#). Detailed descriptions of each study visit can be found in Section [9.5.3](#).

